7.1 Visits and Procedures – main study

The following assessments must be conducted at study visits as per the schedule of assessments:

Finger-stick point of care	At all study visits. This point of care test will be performed using the Xpert®				
testing HCV RNA testing	HCV Viral Load assay on the Gene Xpert® II machine.				
(POC)					
Questionnaires	Behavioural survey, abbreviated behavioural survey and EQ-5D-5L				
Research sample	20mL EDTA and 4mL whole blood at baseline. 10mL EDTA at other study				
	visits if the HCV RNA point of care test is positive or invalid. 10mL EDTA at				
	re-viremia follow up visits.				
HCV sequencing (tested at	For relapse and reinfection as needed.				
Central lab using research					
sample after BSL)					
HCV RNA testing (local	Completed if the point of care test is positive or invalid.				
laboratory)					

The study physician is responsible for the treatment and monitoring of participants and their care. It is recommended that the following assessments are conducted as part of standard treatment monitoring, however this is at the physician's discretion. Any results that are generated from these assessments will be collected as part of the study data.

• Fibroscan or APRI value – within 12 months prior to baseline

The following assessments and procedures must be performed at each visit as specified below.

Baseline visit (Week 0)

- Informed consent
- Medical history
- Study questionnaires (Behavioural and EQ-5D-5L)
- HCV RNA (Finger-stick point of care testing)
- Research sample (20mL EDTA plasma & 4mL whole blood)
- HCV Sequencing (will be performed on the baseline research sample if re-viremia is detected at study follow up visits)

End of Treatment (ETR) – Variable (will depend on selected treatment regimen) (+/-14 days)

- Study questionnaires (Abbreviated Behavioural and EQ-5D-5L)
- HCV RNA (Finger-stick point of care testing)
- Research sample (EDTA plasma) (Only if the HCV RNA point of care test is positive or invalid)
- HCV RNA testing (Local Laboratory) (Only if the HCV RNA point of care test is positive or invalid)

Post Treatment Follow-up Visits

Post Treatment Week 12 (SVR12) – 12 weeks from ETR (+/- 14 days)

- Study questionnaires (Abbreviated Behavioural and EQ-5D-5L)
- HCV RNA (Finger-stick point of care testing)
- Research sample (EDTA plasma)) (Only if the HCV RNA point of care test is positive or invalid)

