10.1 Laboratory supplies and sample processing

Laboratory supplies for collection of research specimens (plasma and whole blood – all sites and PBMCS –

sub-study sites only) will be supplied by the Kirby Institute.

The following blood samples will be collected at time points specified in the schedule of assessments:

1. 10 mL EDTA plasma for HCV RNA testing and future HCV related research (20 mL will be

collected at baseline visit);

2. 4mL whole blood for human genomic DNA analysis collected at the baseline visit only.

Samples will be collected by sites and then processed and stored at -70°C or below at the site local

laboratory for bulk shipment to the Kirby Institute laboratory. Detailed sample processing instructions will

be provided in the laboratory manual.

EDTA plasma samples will be used for study endpoint analysis. HCV viral load will be measured using in-

house and commercial assays. Sequencing of the viral genome will also be performed as a more accurate

means of genotyping. Data generated from the sequencing may also be used to distinguish relapse from

reinfection and to examine the prevalence of mixed infection. Whole blood samples will be used to examine

host factors associated with viral clearance, including but not limited to HLA type, IL28-B, , IP-10, and other

biomarkers.

Sequencing

Sanger sequencing will be performed on all participants with HCV RNA relapse or reinfection in post

treatment follow up to distinguish HCV reinfection from viral relapse (detectable HCV RNA following HCV

virological suppression). Complementary RNA will be generated using SuperScript® VILO™ cDNA Synthesis

Kit (Life Technologies, Carlsbad, CA) with random hexamers. Sequencing of NS5A will be performed on all

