10.3 Future use of biological samples

After the samples have been analysed for the study endpoints as specified in the protocol, remaining samples will be stored for use in future Human Research Ethics Committee approved hepatitis C related research. Samples will be stored until all of the samples have been used up or the sample is no longer viable. Additional consent will not be sought for this storage and future use. It is not optional. Subjects

not wishing to have their samples stored or used in future hepatitis C related research will not be eligible to participate in this study.

11. Statistics

The statistical team and investigators at the Kirby Institute will be responsible for analysing the study data.

Primary Objective:

To evaluate the incidence of HCV reinfection following successful DAA therapy among people with chronic HCV infection and recent injecting drug use.

Hypothesis 1.1: The incidence of HCV reinfection following successful DAA therapy will be <8 per 100 person- yrs among people with recent injecting drug use.

Hypothesis 1.2: HCV reinfection will be associated with ongoing daily injecting drug use, and needle and syringe borrowing, and the treatment in the prison. OST and high-coverage access to needle and syringes will be associated with reduced HCV reinfection.

Outcome: Incidence of HCV reinfection following successful DAA therapy.

Statistical analysis: Rates of HCV reinfection will be calculated using person-time of observation. The estimated date of reinfection will be calculated as the midpoint between the dates of the last undetectable HCV RNA test and the first detectable HCV RNA test at the time of HCV reinfection. Time at risk will commence at the date of undetectable HCV RNA at end of treatment and end at the first of estimated date of re-infection, death, loss-to-follow up or end of study. Confidence intervals for rates will be calculated using a Poisson distribution.

Cox proportional hazards analyses (or other appropriate regression models) will be used to estimate crude and adjusted hazard ratios and corresponding 95% CI to evaluate factors associated with reinfection. Factors hypothesised to be associated with reinfection include demographic factors (age, sex), injecting behaviours (recent injecting drug use, daily injecting, type of drug injected, injecting equipment borrowing), use of needle and syringe programs, and opioid substitution treatment with time-updated co-variates.

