Sample Size: Overall, based on previous reports of HCV reinfection among recent PWID³⁰, and assuming loss to follow-up is 20% per year, it is estimated that the overall reinfection rate will be 8/100 p-yrs (95%CI 5.7-10.7; 478 p-yrs of follow-up; 38 reinfections). Overall (225 with successful therapy, 38reinfections), we will have 80% power to detect a hazards ratio (HR) of 2.47 or greater (with alpha=0.05) for a variable 50% prevalent (e.g. ongoing injecting drug use).

Secondary Objectives:

4) To evaluate the proportion of participants with undetectable HCV RNA at 12 weeks post end of

treatment (SVR12) following DAA HCV therapy among PWID with chronic HCV infection and recent

injecting drug use;

5) To evaluate the proportion of participants who complete treatment;

6) To evaluate the proportion of participants with undetectable HCV RNA at the end of treatment

Hypothesis 2.1: Reduced response to DAA therapy among recent PWID will be predicted by previous

treatment experiences, cirrhosis, baseline mixed HCV infection and resistance associated substitutions.

Outcome: The primary endpoint for this aim is the proportion of participants with a treatment response

(measured by SVR, undetectable HCV RNA 12 weeks after the completion of therapy).

Statistical analysis: The proportion of people with a response to HCV therapy will be evaluated. Factors

associated with treatment response (as measured SVR) will be assessed by univariate and multivariate

logistic regression analyses. Factors hypothesised to be associated with response to DAA therapy are:

injecting behaviours (recent injecting drug use prior to and during treatment and type of drug injected),

clinical factors (opioid substitution treatment, HCV regimen, fibrosis stage), and virological factors (HCV

genotype, baseline mixed HCV infection, presence of resistance associated variants).

Sample size: Assuming an overall SVR of 90% (225 of 250), the 95% confidence intervals (95%CI) around

this estimate will be 86.0 to 92.8%. This study will have robust power to examine the effect of treatment

setting on SVR: e.g. 80% power to detect an odds ratio of 1.87 or greater (alpha=0.05) for a variable that

is 50% prevalent (i.e. community vs. prison).

Collateral research

Objective: To evaluate injecting behaviours and injecting cessation following successful DAA therapy.

Hypothesis: Daily injecting drug use and needle and syringe borrowing will decrease following the initiation

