	bilirubin, total protein
GGT	Gamma Glutamic Transpeptidase
Hgb	Haemoglobin
PWID	People Who Inject Drugs
POC	Point of Care
Reinfection	Detection of infection with an HCV strain which was distinct from the primary
	infecting strain among participants with either spontaneous or treatment-
	induced HCV virological suppression (≤15 IU/ml on Roche TaqMan).
SVR12	Sustained Virological Response, HCV RNA undetectable 12 weeks post-treatment
SVR24	Sustained Virological Response, HCV RNA undetectable 24 weeks post-treatment
WCC	White Cell Count

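### SVR12 counts reinfection before post-treatment week 12 as failed therapy, while the primary analysis counts the same event as reinfection after successful therapy; this mainly dilutes the Hypothesis 2.1 predictors

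*Protocol*

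**What the plan says.** **Response outcome.** Section 11 of the protocol, under the secondary objectives, measures treatment response by SVR: "measured by SVR, undetectable HCV RNA 12 weeks after the completion of therapy". The abbreviations list (section 19) repeats the definition, "Sustained Virological Response, HCV RNA undetectable 12 weeks post-treatment", with no exception for a new strain.

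**Hypothesis and model.** The hypothesis attached to this outcome begins "Hypothesis 2.1: Reduced response to DAA therapy among recent PWID will be predicted by previous" and goes on to treatment experience, cirrhosis, baseline mixed infection and resistance substitutions. The logistic model for SVR has a wider factor list. It includes "injecting behaviours (recent injecting drug use prior to and during treatment and type of drug injected", and also opioid substitution treatment (OST).

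**Reinfection.** For the primary objective, section 11 says: "Time at risk will commence at the date of undetectable HCV RNA at end of treatment". The event is dated at the midpoint between the last negative and first positive RNA test. Section 19 defines reinfection as a strain distinct from the primary one after virological suppression, and does not require SVR12 first. The first scheduled visit after end of treatment is "Post Treatment Week 12 (SVR12) – 12 weeks from ETR (+/- 14 days").

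**Sequencing.** Section 10.1 plans Sanger sequencing for all participants with relapse or reinfection in post-"treatment follow up to distinguish HCV reinfection from viral relapse". No text says how that result enters the SVR outcome or its model.

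**The concern.** The definitions classify one event in two ways. Take a participant who is RNA-negative at end of treatment and first positive at the SVR12 visit, with a distinct strain. The midpoint rule dates the event to about week 6. In the primary analysis it is a reinfection following successful therapy. In the secondary analysis the same person is a failure of therapy. The sample-size text does not settle the matter, because its 225 with successful therapy is the same number as the assumed SVR count (225 of 250).

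Hypothesis 2.1 is about why the drugs fail. Reinfections among the failures are noise with respect to prior treatment, cirrhosis, mixed infection and resistance, and pull those associations towards the null. The model also holds injecting behaviours and OST, which section 11 lists as reinfection factors too. For these the misclassification need not be balanced. The background gives feared lower response and feared reinfection as separate reasons why clinicians hesitate to treat people who inject, so merging the two blurs a distinction that the study was set up to draw.

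**Working it through.** **Inputs from the protocol.** Section 11: 8 per 100 person-years, 478 person-years, 38 reinfections; hazard ratio (HR) 2.47 with 80% power at alpha 0.05 and 50% prevalence; SVR 90% (225 of 250), hence 25 non-responses. Section 1: pooled reinfection rate 2.2 per 100 overall, and 6.4 (upper limit 16.7) with injecting after SVR. Section 7.1: SVR12 at 12 weeks. Assumed: constant hazard, 52.18 weeks per year, two-sided alpha.

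**The plan's own figures.** 0.08 × 478 = 38.2 reinfections, as stated. Power by Schoenfeld's formula: Φ(ln 2.47 × √(38 × 0.25) − 1.96) = Φ(2.79 − 1.96) = 79.6%, against 80% stated. Both reproduce.

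**Reinfections by week 12.** Expected number among the 225 cleared = 225 × (1 − exp(−rate × 12/52.18)).

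| Rate per 100 p-yrs | Events by week 12 | Share of 25 non-responses |
|---|---|---|
| 2.2 | 1.1 | 5% |
| 6.4 | 3.3 | 13% |
| 8 | 4.1 | 16% |
| 16.7 | 8.5 | 34% |

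At 8 per 100 this is also 4.1/38 = 11% of the planned primary events. If 225 is instead the observed SVR count, the number cleared is 225/exp(−0.08 × 12/52.18) = 229.2 (91.7%), and the early reinfections are again about 4.

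**Dilution of a Hypothesis 2.1 predictor.** Assume a 50% prevalent predictor with a true odds ratio (OR) for drug failure of 3.0 and 10% failure overall. Group failure risks are then about 0.054 and 0.146. Multiply both cure probabilities by exp(−0.08 × 12/52.18) = 0.982: SVR becomes 0.929 and 0.838. The OR for non-SVR is (0.162/0.838)/(0.071/0.929) = 2.5.

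**Spurious association with injecting.** Assume 50% exposed, equal 90% cure in both groups (true OR 1.0) and group rates averaging 8 per 100.

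- HR 2.47: rates 11.39 and 4.61; SVR 0.9 × exp(−rate × 12/52.18) = 0.8767 and 0.8905; OR for non-response 1.14.
- HR 5: rates 13.33 and 2.67; OR 1.24.
- All reinfections in the exposed: rates 16 and 0; SVR 0.8675 and 0.9000; OR 1.38.

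Holding total non-responses at 25 instead leaves 20.9 true failures, split evenly, plus 4.1 reinfections. At HR 2.47 this is 13.4/125 against 11.6/125, OR 1.17. With all reinfections in the exposed it is 14.55/125 against 10.45/125, OR 1.44. Over rates of 2.2 to 16.7 per 100 and the three HR settings, the first method gives 1.04 to 1.80. The top value puts the upper confidence limit for people still injecting on the whole cohort and all events in one group.

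**Against the model's precision.** With 25 events split evenly over 125 and 125, SE(log OR) = √(2/12.5 + 2/112.5) = 0.42. So ln 1.17 = 0.16 is about 0.4 SE, and ln 1.44 = 0.36 is just under 0.9 SE.

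**The case against.** The strongest reply is that objective, outcome and model agree with one another. The exploratory objective is factors associated with SVR12, and that is what the model estimates. A breakdown by cause could sit in an analysis plan that is not shown. This stands as a defence of SVR12 and its model, which should stay. It does not resolve the conflict with the primary time-at-risk rule, because the protocol itself fixes both definitions.

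Three stronger readings are tempting, and the documents do not support them.

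- *Hypothesis 2.1 is biased by injecting.* The hypothesis does not name injecting. That association arises only from the factor list, and the covariates there cover injecting before and during treatment. Everyone had injected in the six months before enrolment, so contrast on prior injecting is limited. The covariates only correlate with injecting after treatment, so the ORs above, which let the HR act on the covariate itself, overstate the effect. HR 2.47 is also a detectable effect from a power statement, not an expected one.
- *All 250 are at risk.* That would give 250 × (1 − exp(−0.08 × 12/52.18)) = 4.6 events (18%), but people whose infection was not cleared are not at risk of reinfection.
- *Sequencing will not be used for this endpoint.* The protocol is silent on the link. The SVR12 visit is a post-treatment visit, so the sequence data should exist.

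A further objection concerns the remedy and stands. If failure were limited to relapse with the baseline strain, a minor strain of a baseline mixed infection, missed by Sanger sequencing and re-emerging later, would look like reinfection and leave the failure group. Mixed infection is a named Hypothesis 2.1 predictor, and full-length next-generation sequencing is only optional. A simple replacement of the outcome would therefore harm that hypothesis.

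**Conclusion.** The point holds in a limited form. As defined, SVR12 counts reinfection by week 12 as failure of therapy, and the primary analysis counts the same event as reinfection after success. At 8 per 100 person-years about 4 of 25 planned non-responses (16%) are affected, with a range of 5% to 34% over the rates that the protocol cites. The hypothesised incidence is below 8, so the lower part of that range matters.

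The main consequence is dilution of the predictors that Hypothesis 2.1 names (OR 3.0 to about 2.5 under the stated assumptions). A spurious association of injecting or OST with response is possible but modest: about 1.14 to 1.17 at HR 2.47, at most about 1.4 at the planned rate, and smaller in practice. A bias of this size would rarely change a conclusion on injecting by itself. The figures rest on a constant hazard from end of treatment and on each early reinfection still being viraemic at week 12.

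**What to change.** 1. Keep SVR12 and its logistic model as stated.
2. State that a participant undetectable at end of treatment with sequence-confirmed reinfection by the SVR12 visit is tabulated as a separate category. Report SVR12 both ways: reinfection as non-SVR, and reinfection as cure of the original infection.
3. Add a Hypothesis 2.1 model with virological failure (on-treatment non-response or relapse) as the outcome. Confirmed reinfections are not failures in it.
4. In that model, keep as failures any recurrence that could not be sequenced, and any in which a minor strain of a baseline mixed infection cannot be ruled out. Run a sensitivity analysis that classifies these the other way.

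The cost is outcome wording, one table and one added model with its sensitivity analysis. Sequencing of these recurrences is already planned, no visits or samples are added, and the primary endpoint does not change. The added model has slightly fewer events (25 − 4.1, about 21), and some mixed infections will still be misclassified.

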Participants who have a positive HCV RNA point of care test during the follow up period will be considered to have post-treatment recurrence of viremia. All patients identified as having post-treatment recurrence of viremia will have an increased follow up schedule for 8 weeks before returning to the standard follow up schedule. Participants once identified as having recurrent viremia will be followed intensely for 8 weeks as per the post-treatment recurrence of viremia schedule of assessments. Once the participant has completed 8 weeks follow up they will continue with 3 monthly follow up visits as per the standard schedule of assessments.

Patients may be offered retreatment with government approved DAA drug regimens. The decision to retreat as well as the regimen and duration will be determined by the treating clinician according to government prescribing guidelines.

[figure not shown]

Figure 2: SHARP-C post-treatment recurrence of viremia schema

6. Treatment of participants

A total of 250 participants will be enrolled with chronic HCV, recent injecting drug use (past 6 months) and initiating DAA HCV therapy. Participants will be seen in hospital-based HCV and community-based drug treatment clinics.

Participants will be treated with a government approved DAA drug regimen which will be prescribed as appropriate for the participants fibrosis stage, HCV genotype and previous treatment experience at the discretion of the treating clinician.

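### The SVR sample-size paragraph claims 80% power for an odds ratio of 1.87; its own inputs give about 31%, and the detectable odds ratio is about 3.5

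*Protocol*

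**What the plan says.** Protocol section 6 sets the enrolment: "A total of 250 participants will be enrolled with chronic HCV, recent injecting drug use (past 6 months) and initiating DAA HCV therapy". In section 11, the sample-size paragraph under the secondary objectives starts from "Assuming an overall SVR of 90% (225 of 250") and says that the 95% confidence limits around "this estimate will be 86.0 to 92.8"%. It then describes the power to study treatment setting as robust and gives an example: "80% power to detect an odds ratio of 1.87 or greater (alpha=0.05) for a variable that" "is 50% prevalent (i.e. community vs. prison"). The analysis named just above is univariate and multivariate logistic regression of SVR on injecting behaviour, clinical factors and virological factors. Hypothesis 2.1, in the same part of section 11, predicts a reduced response with previous treatment, cirrhosis, mixed infection and resistance-associated substitutions.

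**The concern.** At 90% SVR, 250 participants yield about 25 treatment failures. Power for a binary outcome depends mainly on the number in the rarer category, and 25 events are far too few to detect an odds ratio below 2 with 80% probability. The printed confidence limits also look off: 92.8% is lower than the usual upper limits for 225 of 250.

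What is at stake is the reading of a null result. Someone who accepts 80% power at 1.87 would take a non-significant comparison as fair evidence that no moderate association exists. The sentence is about treatment setting, but it is the only power statement given for any SVR comparison, so it is likely to be carried over to the other listed factors. Factors present in much less than half the cohort, or adjusted for other factors, would have less power than the balanced case worked here.

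**Working it through.** **Inputs, all from the protocol.** N = 250 (sections 6 and 11); overall SVR 90%, 225 of 250 (section 11); variable 50% prevalent, so 125 per group; alpha 0.05. Sidedness is not stated: two-sided is assumed, and one-sided is shown as a variant.

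**Step 1: group SVRs implied by an odds ratio of 1.87.** Solve (p1 + p2)/2 = 0.90 and [p2/(1 − p2)] / [p1/(1 − p1)] = 1.87. This gives p1 = 0.8725 and p2 = 0.9275, a difference of 0.0550.

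**Step 2: attempt to reproduce the stated 80%.** Two-proportion test with pooled variance under the null:

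- SE under the null = √(2 × 0.90 × 0.10 / 125) = 0.03795
- SE under the alternative = √[(0.8725 × 0.1275 + 0.9275 × 0.0725) / 125] = 0.03779
- z = (0.0550 − 1.96 × 0.03795) / 0.03779 = −0.51
- Power = Φ(−0.51) = 30.4%

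Exact enumeration of the chi-square test gives 30.6%. The stated 80% is not reproduced.

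**Step 3: other readings of the inputs at odds ratio 1.87, N = 250.**

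| Reading | Two-sided power | One-sided power |
|---|---|---|
| 90% is the overall SVR | 30% | 42% |
| 90% is the better group (other 82.8%) | 38% | 51% |
| 90% is the worse group (other 94.4%) | 25% | 36% |
| Overall SVR 50% (contradicts the protocol) | 69% | 79% |

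Only the last cell comes near 80%. It needs both a one-sided test and a 50% response rate. The logistic-regression approximation, with the same two changes, gives a detectable odds ratio of 1.876.

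**Step 4: odds ratio detectable with 80% power, two-sided, overall SVR 90%.**

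- Exact enumeration: power is 79.9% at 3.5 (SVR 84.9% against 95.1%)
- Normal approximation: 3.65
- Logistic-regression approximation: exp[(1.96 + 0.842) / √(250 × 0.25 × 0.09)] = exp(2.80 / 2.372) = 3.26

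If 90% is assigned to the better group the figure is 2.7; if to the worse group, 6.4.

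**Step 5: N needed for 1.87 with 80% power.** Per group: [1.96 × √(2 × 0.90 × 0.10) + 0.842 × √(0.8725 × 0.1275 + 0.9275 × 0.0725)]² / 0.0550² ≈ 465.5, or about 931 in total (1,004 with continuity correction).

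**Step 6: 95% interval for 225 of 250.**

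| Method | Limits (%) |
|---|---|
| Protocol | 86.0 to 92.8 |
| Exact (Clopper-Pearson) | 85.6 to 93.4 |
| Wilson | 85.7 to 93.1 |
| Wald | 86.3 to 93.7 |
| Jeffreys | 85.8 to 93.3 |

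Every upper limit is at least 93.1%. The stated width is 92.8 − 86.0 = 6.8 points; the exact width is 93.4 − 85.6 = 7.8. The printed interval is close to Wilson at N = 300 (86.1 to 92.9).

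**Step 7: a check on the neighbouring claim.** The hazard-ratio statement for the primary objective does reproduce. With 38 events and 50% prevalence, exp[2.80 / √(38 × 0.25)] = 2.48 against the stated 2.47. The problem is confined to the SVR paragraph.

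**The case against.** The arithmetic is hard to contest, but several points can be made about its weight.

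- The claim of robust power names treatment setting, not every SVR predictor. That is so, and this write-up does not attribute a wider claim to the protocol. The stated 80% is still wrong for the one comparison it names.
- That comparison is community against prison, whereas section 4 recruits only from hospital-based and community drug treatment clinics. With no prison setting described, the illustrated 50% split has no counterpart in this study. This does not rescue the power figure; it is a further reason to rewrite the sentence.
- Section 3 already lists factors associated with SVR12 as an exploratory objective. True, but section 5 puts predictors of non-response under the secondary objective, and section 11 treats them under the secondary objectives with a power claim. The labelling is not uniform.
- Sidedness is unstated, and a one-sided test at 50% response gives 79%. That contradicts the protocol's own 90%; at 90% overall, one-sided power is 42%.
- The interval error is under one point at either limit and changes no conclusion. Accepted.
- Nothing in the protocol derives the 250 from this odds ratio, and the primary incidence objective does not depend on it. Also accepted. The error concerns what the study may claim for a secondary analysis.

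**Conclusion.** The concern holds. For 250 participants, 90% overall SVR, a 50% prevalent variable and a two-sided 5% test, power at an odds ratio of 1.87 is about 31% rather than 80%. The detectable odds ratio is about 3.5 (3.3 to 3.7 by formula), and no reading that keeps SVR at 90% comes near the stated figure. The detectable value does depend on which group carries the 90%, but 1.87 fails each way. The confidence interval is also wrong, by less than one point, and is a minor correction. The SVR proportion itself is still estimated to within about 4 points, and the primary objective is untouched. The statement about power should not stand, because it misdescribes what a null SVR comparison would mean.

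**What to change.** Rewrite the sample-size paragraph for the secondary objectives in section 11 along these lines:

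> With 250 participants and an SVR of 90%, the exact 95% confidence interval is 85.6% to 93.4%. For a factor present in half of participants, a two-sided 5% test has 80% power for an odds ratio of about 3.5 (SVR of about 85% against 95%); power for an odds ratio of 1.87 is about 31%. Analyses of factors associated with SVR are exploratory.

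Delete the description of the power as robust. Remove the community-against-prison example, or replace it with a contrast that the recruiting sites can supply, using that contrast's expected prevalence in the calculation. Make the exploratory label consistent across sections 3, 5 and 11.

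The cost is protocol wording only. Enrolment, endpoints and analysis methods stay as they are; the stated detectable effect becomes less favourable.
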